### **7.4. Secondary objectives**

To describe any associations between number of doses of antimicrobial prophylaxis or presence of an allergy label and the following:

- Antimicrobial side effects
- Postoperative infections
- Other complications (listed in appendix)
- Mortality at 30 days after surgery

### **7.5. Secondary outcome measures**

- Number of antimicrobials to treat an infection
- Incidence of antimicrobial side effects within 30 days after surgery:
  - Acute kidney injury of any cause
  - Diarrhoeal illness of any cause

- Hearing loss, tinnitus or vertigo of any cause
- Suspected allergic reaction to antimicrobials
- Suspected allergic reaction to any other drug
- Incidence of postoperative infection within 30 days after surgery
- Incidence of all postoperative complications within 30 days after surgery
- Mortality at 30 days

### **7.6. Process measures**

- Duration of hospital stay (number of days from surgery until hospital discharge)
- Critical care admission (level two or level three)\*
- Duration of critical care days (level two or level three)\*

\*A full list of definitions is available in the appendix A

### **7.7. Inclusion criteria**

Adult patients aged 18 years and over undergoing one of the following surgical procedures:

- Primary hip or knee replacement
- Internal fixation of a closed long bone fracture (upper or lower limb)
- Colorectal resection
- Trans-urethral resection of prostate or bladder tumour
- Caesarean section
- Hysterectomy (vaginal or abdominal)

### **7.8. Exclusion criteria**

- Use of antibiotics in the two weeks prior to surgery
- Previous participation in the study

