## **7. Study Objectives**

### **7.1. Exposures of interest**

- Number of doses of antimicrobial drugs administered as prophylaxis before, during or after surgery to prevent an infection
- Label of allergy to any drug

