## 8.3. Study data

Data will be collected on all eligible patients who undergo surgery during the study recruitment period. Only routine clinical data will be included and where this is unavailable the domain will be left blank.

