#### *Surgical site infection (organ space)*

An infection at the surgical incision site involves any part of the body, excluding the skin incision, fascia, or muscle layers, that is opened or manipulated during the operative procedure and the patient has at least one of the following:

- purulent drainage from a drain that is placed through a stab wound into the organ/space.
- organisms isolated from an aseptically obtained culture of fluid or tissue in the organ/ space.
- an abscess or other evidence of infection involving the organ/space that is found on direct examination, during reoperation, or by histopathologic or radiologic examination.
- diagnosis of an organ/space surgical site infection by a surgeon or attending physician.

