### *Urgent surgery*

Acute onset or deterioration of conditions that threaten life, limb or organ survival;  
fixation of fractures; relief of distressing symptoms.

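### Infection already present at the index operation is neither excluded nor set aside in the SSI definitions, and the direction of the resulting bias depends on which exposure wording is followed

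*Protocol*

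**What the plan says.** Eligibility in Protocol 7.7 rests on age and procedure: "Adult patients aged 18 years and over undergoing one of the following surgical procedures". Colorectal resection, caesarean section and hysterectomy carry no limit on indication or urgency. Fracture fixation is limited to closed fractures. Section 7.8 has two exclusions, "Use of antibiotics in the two weeks prior to surgery" and "Previous participation in the study". Section 8.3 adds: "Data will be collected on all eligible patients who undergo surgery during the study recruitment period". Appendix A defines urgent surgery, beginning "Acute onset or deterioration of conditions that threaten life, limb or organ survival", so non-elective cases are foreseen.

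The exposure is worded in two ways. Section 7.1 gives "Number of doses of antimicrobial drugs administered as prophylaxis before, during or after surgery to prevent an infection". Sections 7.4 and 9 also speak of prophylaxis, and 7.5 lists antimicrobials used to treat infection separately, as a secondary outcome. The primary objective in 7.2 and the first synopsis objective refer more broadly to perioperative antimicrobial drugs, without limiting them to prophylaxis.

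The primary outcome in 7.3 is SSI within 30 days after surgery. One of the organ/space criteria in Appendix A is "organisms isolated from an aseptically obtained culture of fluid or tissue in the organ/ space". None of the three SSI definitions says how to handle infection found at the index operation.

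**The concern.** A study of prophylaxis needs patients whose operative site is free of infection when surgery starts. The antibiotic exclusion does not secure this, because it selects on when treatment began and not on whether infection was present. Take a patient with a perforated colon or an intrauterine infection. If treated the day before, the patient is dropped; if first treated at theatre, the patient is kept. Nor does 7.8 say how doses on the day of surgery are handled, although 7.1 counts prophylaxis given before the operation.

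For those who stay in, the 30-day window limits the timing of an SSI but not its origin. A positive organ/space culture in the first days after surgery could come from the original infection and still meet the definition. The same infection determines how many doses the patient receives. It is therefore linked to both exposure and outcome, and a small group with unusual dose counts has high leverage in a model with a per-dose slope.

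**Working it through.** **Step 1: reproduce the planned effect and sample size.** Inputs from Protocol section 9: dose Poisson with mean 2; SSI risk 12% at dose 0 and 10% at dose 2; logit linear in dose; 90% power; 5% significance (two-sided assumed).

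- logit(0.12) = ln(0.12/0.88) = −1.992; logit(0.10) = ln(0.10/0.90) = −2.197.
- Slope β = (−2.197 + 1.992)/2 = −0.102, so the odds ratio is exp(−0.102) = 0.903 per dose.
- N = (1.960 + 1.282)² × V/β². V = 6.023 is the slope element of the inverse per-patient Fisher information under Poisson(2). N = 10.507 × 6.023/0.010485 = 6,036, against 6,000 stated. Power at 6,000 is 89.8% by formula and 91.6% by simulation (1,500 runs).

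The stated sample size reproduces and is not affected by this point.

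**Step 2: add patients infected at surgery.** Assumptions, none of them in the documents: a share f of the cohort is infected at the start of surgery; their recorded SSI risk is r; their counted doses are Poisson with mean m. Everyone else follows the planning model. With w(d) the mixture probability of dose d and y(d) the mixture SSI risk at that dose, the large-sample logistic fit of SSI on dose solves Σ w(d)[y(d) − expit(α + βd)] = 0 and Σ d·w(d)[y(d) − expit(α + βd)] = 0.

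Fitted odds ratio per dose (0.903 with no infected patients):

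| Doses counted | m | f = 1%: r = 20 / 30 / 40% | f = 3%: r = 20 / 30 / 40% |
|---|---|---|---|
| Treatment included | 4 | 0.917 / 0.928 / 0.939 | 0.943 / 0.973 / 1.001 |
| Treatment included | 6 | 0.932 / 0.952 / 0.972 | 0.976 / 1.024 / 1.068 |
| Treatment included | 10 | 0.959 / 0.993 / 1.024 | 1.015 / 1.067 / 1.112 |
| Prophylaxis only | 0 | 0.895 / 0.885 / 0.876 | 0.881 / 0.855 / 0.830 |
| Prophylaxis only | 1 | 0.899 / 0.895 / 0.890 | 0.893 / 0.880 / 0.868 |
| Prophylaxis only | 2 | 0.904 / 0.905 / 0.906 | 0.908 / 0.910 / 0.912 |

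**Step 3: read the table.** With treatment doses counted, infected patients are high-dose and high-event, and the odds ratio moves towards 1 or above it. It reaches 1 or more in one of nine scenarios at 1% infected and in six of nine at 3%. With prophylaxis only, infected patients with fewer doses than average (m = 0 or 1) make the association look more protective than planned. If they have the same mean as everyone else (m = 2), the shift is at most 0.912 − 0.903 = 0.009.

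**The case against.** The strongest reply is that the section defining the exposure, 7.1, limits it to prophylaxis. Sections 7.4 and 9 use the same term, and 7.5 puts treatment antimicrobials among the outcomes. A reader might infer from 7.2 and the synopsis that treatment of an existing infection is analysed as prophylaxis and that the planned association is therefore reversed. The documents do not support that as a statement of fact. It requires the broader wording to prevail over 7.1, or misclassification when notes are abstracted. Under 7.1 the shift is small or in the other direction.

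Other parts of the reply also have weight. The two-week exclusion, read literally, removes infected patients treated before theatre, possibly many of them. Primary joint replacement and closed fracture fixation offer little obvious route to infection at surgery, so a cohort-wide 3% may be high. The fit above has one covariate, whereas section 9 plans multivariable models. The SAP is not shown and could restrict the analysis set or adjust for wound contamination. Reading the restriction to closed fractures as an infection-free principle is also only an inference, since the protocol gives no reason for it.

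The gap itself remains. Eligibility is fixed in the protocol, and the SSI definitions do not separate persisting from new infection. An SAP can remove these patients only if infection at surgery is recorded, and the protocol does not name that item. That the synopsis describes sites as undertaking elective surgery is weak protection, because caesarean section and fracture fixation are eligible and urgent surgery is defined.

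**Conclusion.** The point holds in a limited form. Patients infected at the start of the index operation and first treated at or around theatre are eligible. Their infection may be recorded as SSI, and the protocol's exposure wordings differ on whether their treatment doses count.

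The size is conditional. With 1 to 3% infected and 20 to 40% recorded SSI, both assumed, the planned 0.90 per dose becomes about 0.92 to 1.11 if treatment doses are counted (assumed mean 4 to 10). It becomes about 0.83 to 0.91 if only prophylactic doses are counted (assumed mean 0 to 2). The direction of bias thus depends on the reading, and reversal occurs only in some of the scenarios that count treatment doses. This is worth correcting because the correction is cheap and protects the primary association, but it does not show that the planned analysis must fail.

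**What to change.** Add to 7.8 and to the synopsis an exclusion for known or suspected infection at the operative site or in the operated organ at the start of surgery. If patients are already enrolled, flag these cases from the operation note, remove them from the primary analysis set and report the number removed by procedure. Reword 7.2 and the first synopsis objective to agree with 7.1, so that the primary exposure is prophylactic doses only.

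The cost is one line of text and one extra item from notes that 8.4 already has the research team review. At the assumed 1 to 3%, the loss from the planned 13,720 is about 137 to 412 patients (13,720 × 0.01 and × 0.03), leaving at least 13,308, well above the 6,000 required for the dose analysis. The results would no longer cover surgery for established infection.

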### **7.2. Primary objective**

To identify any associations between the type and number of doses of antimicrobial drugs administered during the perioperative period and the incidence of surgical site infection within 30 days after surgery.

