## **9. Statistical Considerations**

We will use a pre-specified statistical analysis plan. The sample size required to detect an association between SSI and dose was calculated using the 'simsam' package in STATA (Version 17.0), which uses simulation. We assumed that dose was a Poisson random variable with mean and variance 2, and that there was a linear relationship between  $\log(p/(1-p))$  and dose, where  $p$  is the risk of SSI. To specify the association we would like power to detect we specified the SSI risk at the mean dose (10%) and the SSI risk at dose 0 (12%), which then determines the coefficients in the linear relationship between  $\log(p/(1-p))$  and dose. To demonstrate an association between dose and SSI risk using logistic regression, with 90% power at the 5% significance level, we require 6000 patients. Also, to demonstrate an association between allergy label (binary exposure) and complications. The incidence of complications in exposed 15% and unexposed 10%, with 80% power at the 5% significance level we require 1372 patients. However, we expect only 10% of the sample to have an allergy label, so the total sample size would need to be 13720. Considering both sample size calculations for our primary and principal secondary outcomes we aim to recruit a total 13720 patients.

The primary analysis will test associations between antimicrobial prophylaxis and surgical site infection. Secondary analyses will examine the association between the type and number of doses of antimicrobial prophylaxis and potential antibiotic-related harms (including allergic reactions, acute kidney injury, diarrhoeal illness within 30 days after surgery), as well as other postoperative infective complications within 30 days after surgery, and mortality at 30 days. In addition, we will examine any associations between the presence of drug allergy labels and SSI, other postoperative infections and antibiotic-related complications. We will report continuous variables as mean with standard deviation or median with interquartile range. We will use multivariable regression analysis to test associations between exposure and outcome measures, adjusting for pre-specified covariates that are plausibly associated with both exposure and outcome. We will use logistic regression models for binary outcomes and linear regression models for continuous outcomes. The threshold for statistical

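### The two-week antibiotic exclusion has no exemption for index-operation prophylaxis, so a preoperative prophylactic dose is both the exposure and a reason for exclusion

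*Protocol*

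**What the plan says.** Protocol section 7.8 lists as an exclusion "Use of antibiotics in the two weeks prior to surgery", and the synopsis (section 4) uses the same words. Neither place states a purpose (treatment or prophylaxis), an exception, or the moment at which the two-week window ends.

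Section 7.1 gives the first exposure of interest as "Number of doses of antimicrobial drugs administered as prophylaxis before, during or after surgery to prevent an infection". The primary objective in section 7.2 begins "To identify any associations between the type and number of doses of antimicrobial drugs administered during the perioperative period". The outcome named there is surgical site infection (SSI) up to day 30.

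Neither the glossary nor the definitions in Appendix A reconcile the two texts. Section 8.3 limits data collection to eligible patients.

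**The concern.** A prophylactic dose given before the index operation meets the definition in 7.1 and also triggers the exclusion in 7.8. Eligibility then depends on the variable whose association with SSI the study sets out to estimate.

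If every site resolved the conflict in the same way, the harm would be limited to how the cohort is described. The risk is that they do not. A dose given well before the operation could be counted at one hospital and lead to exclusion at another. The recorded dose distribution would then partly reflect local reading of 7.8.

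Selection on a correctly modelled dose count alone would mainly cost precision. Here, however, selection would act on the timing of doses and on site, and either may be related to SSI risk. Bias is then possible, and its direction cannot be worked out from the protocol.

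The protocol has little that would reveal this. Section 12.2 checks submitted data, which excluded patients never enter. Section 13 says that collection at individual hospitals is not routinely monitored and that there is no source data verification. No record of patients excluded at screening is described.

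**Working it through.** **1. The texts side by side.** Take a patient given one prophylactic dose before the index operation.

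- Under 7.1 the dose count is at least 1, so the patient is exposed.
- Under 7.8 an antibiotic was used within the two weeks before surgery, so the patient is excluded.
- A patient dosed only during or after surgery is exposed under 7.1 and is not excluded under 7.8.

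The conflict therefore concerns preoperative doses only.

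**2. The plan's own figure.** Section 9 states "We assumed that dose was a Poisson random variable with mean and variance 2", with SSI risk 12% at dose 0 and 10% at the mean dose. The 5% level is taken as two-sided, which the protocol does not state.

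- Intercept: a = ln(0.12/0.88) = −1.992.
- Slope: b = [ln(0.10/0.90) − a]/2 = −0.1024, an odds ratio of 0.903 per dose.
- With weights v_k = P(dose = k)·p_k(1 − p_k), Var(b) = Σv / {n[Σv·Σvk² − (Σvk)²]}, and power = Φ(|b|/SE − 1.96).
- Result: n = 6,036 for 90% power, and 89.8% power at n = 6,000. A simulation of 1,500 logistic fits at n = 6,000 gave 91.1%.

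The protocol's statement, "with 90% power at the 5% significance level, we require 6000 patients", is reproduced. The overall target of 13,720 comes from the allergy-label calculation (1,372/0.10) and is not affected by this point.

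**3. Expected number exposed.** P(at least one dose) = 1 − exp(−2) = 86.5%. Of 13,720 patients, about 11,863 would have a dose at some time and about 1,857 would have none.

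**4. Bounds on the literal reading.** Let q be the share of exposed patients with at least one preoperative dose. The protocol does not give q, so the whole range is shown. The table takes 13,720 as the number before this exclusion. It also assumes that removal is unrelated to how many doses an exposed patient had, and it uses the unadjusted model of step 2.

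| q (assumed) | Excluded (q × 11,863) | Kept | Exposed kept | Power, dose–SSI |
|---|---|---|---|---|
| 0% | 0 | 13,720 | 11,863 | 99.8% |
| 25% | 2,966 | 10,754 | 8,897 | 99% |
| 50% | 5,932 | 7,788 | 5,932 | 97% |
| 75% | 8,897 | 4,823 | 2,966 | 87% |
| 90% | 10,677 | 3,043 | 1,186 | 61% |
| 95% | 11,270 | 2,450 | 593 | 39% |
| 100% | 11,863 | 1,857 | 0 | not estimable |

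If sites kept recruiting until 13,720 were enrolled, numbers would be restored but composition would not. At q = 90% the exposed share would be 1,186/3,043 = 39%, against 86.5% in the planning model.

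**The case against.** The strongest reply is that nobody would apply the criterion literally. Prophylaxis is the subject of the study (sections 6.2, 7.1, 7.2 and 9), and excluding those who received it before surgery would defeat the purpose. The vocabulary also differs: 7.1 speaks of antimicrobial drugs given as prophylaxis, 7.8 of antibiotics in a two-week window. In the schedule (section 8.2) eligibility is checked in a screening column that stands ahead of the preoperative column, so prophylaxis given at operation would normally come after the check.

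Most of this stands as evidence of intent: the criterion was probably meant for earlier antibiotic courses. It does not remove the conflict. Screening has no stated time, and no text says where an earlier course ends and index prophylaxis begins. Doses given some time before the operation remain open to either reading.

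Two stronger readings are tempting, and the protocol supports neither.

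- A reader might infer that the rule removes the exposed patients altogether, some 86% of the cohort. That figure counts doses at any time. Patients dosed only during or after surgery stay in, so total loss follows only if q = 100%.
- A reader might infer that the loss falls mainly on one procedure, such as colorectal resection with oral prophylaxis beforehand. The protocol mentions no such regimen and gives neither preoperative dosing nor SSI risk by procedure, so no figure can be attached to that.

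**Conclusion.** The contradiction is real and should be corrected. It is a defect of wording in a rule that the protocol itself fixes, so it is not a detail that can be left to the statistical analysis plan. Patients turned away at screening are not in the data, and no later analysis rule can bring them back.

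Its size cannot be stated as a single number. The table bounds the literal reading, from no loss at q = 0% to an association that cannot be estimated at q = 100%, and it does not forecast what sites will do. The realistic harm is uneven handling of earlier preoperative doses between hospitals. That is a possibility the wording allows, not something the protocol shows will happen, and a larger sample would not cure it. The stated sample sizes are reproduced and are not in dispute.

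**What to change.** Keep the present criterion in section 7.8 and the synopsis, and add: *other than prophylaxis for the index procedure, which is counted as exposure*. State in the same place when the preoperative window ends, so that sites apply one cut-off.

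Do not reword the exclusion to cover treatment courses only. That would newly admit patients on long-term antibiotics, or given prophylaxis for a different procedure within the two weeks. The current text excludes both, and the conflict does not require that change.

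The cost is one clause and one definition in two places, plus a note to sites. The 6,000 and 13,720 figures stay as they are. The change concerns entry to an observational cohort and alters no patient's treatment.

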## **8. Study Design**

Multi-centre observational cohort study.

### **8.1. Recruitment and informed consent**

Patient consent will not be required on the basis that the dataset will only include variables documented as part of routine clinical care and that identifiable patient data

will not leave the hospital where each individual patient is treated. Only anonymised or coded data will be provided to the SAPPHIRE study group.

## 8.2. Schedule of assessment

Event/ Visit	Screening	Before surgery	After surgery	Hospital discharge	30 days after surgery
Inclusion/ exclusion criteria	x				
Medical history		x			
Demographic information		x			
Review of medical notes		x	x	x	x
Preoperative information		x			
Intraoperative information			x		
Postoperative information			x		
Details of hospital stay				x	
End of study					

## 8.3. Study data

Data will be collected on all eligible patients who undergo surgery during the study recruitment period. Only routine clinical data will be included and where this is unavailable the domain will be left blank.

## 8.4. Data collection

A standardised data set will be collected for each patient recruited by the study investigator in all participating hospitals. The patient's medical records will be reviewed by a member of the research team, and identify significant events during the admission. The primary outcome assessment will occur at 30 days after the index surgical procedure. Data will be uploaded directly onto a bespoke and secure online database held by Barts London NHS Trust.

### **8.5. End of study definition**

The end of the study is defined as the end of the 30-day follow-up for the last patient enrolled in the study.

## **9. Statistical Considerations**

We will use a pre-specified statistical analysis plan. The sample size required to detect an association between SSI and dose was calculated using the 'simsam' package in STATA (Version 17.0), which uses simulation. We assumed that dose was a Poisson random variable with mean and variance 2, and that there was a linear relationship between  $\log(p/(1-p))$  and dose, where  $p$  is the risk of SSI. To specify the association we would like power to detect we specified the SSI risk at the mean dose (10%) and the SSI risk at dose 0 (12%), which then determines the coefficients in the linear relationship between  $\log(p/(1-p))$  and dose. To demonstrate an association between dose and SSI risk using logistic regression, with 90% power at the 5% significance level, we require 6000 patients. Also, to demonstrate an association between allergy label (binary exposure) and complications. The incidence of complications in exposed 15% and unexposed 10%, with 80% power at the 5% significance level we require 1372 patients. However, we expect only 10% of the sample to have an allergy label, so the total sample size would need to be 13720. Considering both sample size calculations for our primary and principal secondary outcomes we aim to recruit a total 13720 patients.

The primary analysis will test associations between antimicrobial prophylaxis and surgical site infection. Secondary analyses will examine the association between the type and number of doses of antimicrobial prophylaxis and potential antibiotic-related harms (including allergic reactions, acute kidney injury, diarrhoeal illness within 30 days after surgery), as well as other postoperative infective complications within 30 days after surgery, and mortality at 30 days. In addition, we will examine any associations between the presence of drug allergy labels and SSI, other postoperative infections and antibiotic-related complications. We will report continuous variables as mean with standard deviation or median with interquartile range. We will use multivariable regression analysis to test associations between exposure and outcome measures, adjusting for pre-specified covariates that are plausibly associated with both exposure and outcome. We will use logistic regression models for binary outcomes and linear regression models for continuous outcomes. The threshold for statistical

significance will be 5%. We will handle missing data according to a pre-specified plan, based on the type and amount of missing data. Our main strategies will be list-wise deletion and multiple imputation. Data will be analysed using STATA version 14 or R. Analysis code will be published in a supplementary appendix to any manuscript.

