#### 4. Summary and Synopsis

Short title	SAPPHIRE study
Methodology	National, multi-centre prospective observational cohort study collecting only anonymised data
Research sites	NHS hospitals undertaking elective surgery as listed above
Objectives	
 
1. To identify association between the use of perioperative antimicrobial drugs and the incidence of postoperative surgical site infection.
 
2. To identify association between the use of perioperative antimicrobial drugs and other perioperative complications.
 
3. To identify association between antimicrobial allergy labels and perioperative complications.
 

Number of participants	13,720 patients data sets
Inclusion criteria	
Adult patients (aged <math>\geq 18</math> years) undergoing one of the following surgical procedures:
 
 
• Primary hip or knee replacement
 
• Internal fixation of a closed long bone fracture (upper or lower limb)
 
• Colorectal resection
 
• Trans-urethral resection of prostate or bladder tumour
 
• Caesarean section
 
• Hysterectomy (vaginal or abdominal)
 

Exclusion criteria	
 
• Use of antibiotics in the two weeks prior to surgery
 
• Previous participation in the study
 

Statistical methodology and analysis	
Continuous variables will be reported as a mean with standard deviation or median with interquartile range. Multivariable regression analysis will be used to test associations between exposure and outcome measures, adjusting for pre-specified covariates that are plausibly associated with both exposure and outcome. Logistic regression models will be used for binary outcomes and linear regression models for continuous outcomes. The threshold for statistical significance will be 5%. A single final analysis is planned at the end of the study.

Study duration	31 months
----------------	-----------

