The side effects and harms caused by antimicrobial drugs can be substantial, with 1 in 50 surgical patients suffering complications directly attributable to antimicrobial use including acute kidney injury, hearing loss and anaphylaxis. A recent national audit identified antimicrobials as the single commonest cause of life-threatening allergic reactions during surgery. In addition, self-reported antimicrobial allergy can lead to harm from the use of alternative antimicrobial drugs that are less effective and more toxic. Up to 1 in 7 patients carries such a label, although a diagnosis of allergy has rarely been proven through specialist allergy investigation. Previous work has demonstrated that the most common antibiotic allergy is to penicillin, with this label carried by 12% (2624/21,224) of elective surgical patients in the UK. Of such patients, half received second-line antimicrobial drugs and 40% received either no prophylaxis,

or a drug not recommended by local guidelines. Based on these findings, an estimated 100,000 patients every year may be unnecessarily denied penicillin-based antibiotics. Avoidance of penicillin is a recognised cause of harm in a variety of patient groups, associated with increased nosocomial infections, increased wound infections, and higher mortality. Other research has demonstrated increased length of stay for mixed populations of hospital in-patients. The scale of this problem is unknown because there is no system to report antimicrobial use and its associated harms.

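### The 13,720 target divides a two-group total by 10%, so the stated 80% power does not belong to it; the same formula at a 1:9 split needs about 3,580

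*Protocol*

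**What the plan says.** Section 9 (Statistical Considerations) of the protocol contains two sample size calculations.

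- Primary, number of prophylaxis doses and surgical site infection, by simulation: "with 90% power at the 5% significance level, we require 6000 patients".
- Principal secondary, complications by presence of an allergy label: "The incidence of complications in exposed 15% and unexposed 10%, with 80% power at the 5% significance level we require 1372 patients".

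The second is then scaled up: "However, we expect only 10% of the sample to have an allergy label, so the total sample size would need to be 13720". Section 9 says that both calculations were considered and adopts 13,720 as the recruitment target. The synopsis in Section 4 repeats it as "13,720 patients data sets".

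The expected 10% label prevalence is the only reason given for the tenfold increase. Clustering by hospital, covariate adjustment, missing data and rarer outcomes are not offered as a basis for it.

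**The concern.** Dividing a required number by a prevalence is valid only if that number counts exposed patients alone. If 1,372 is the total over both groups, half of it is already unlabelled, and dividing the whole by 10% produces a design to which the stated 80% does not apply.

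This step fixes the headline recruitment target, since the other calculation asks for fewer than half as many patients. If it is wrong, the target has no valid stated justification, and an incorrect power statement would pass into the study report.

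**Working it through.** **Inputs** (protocol, Section 9): p1 = 0.15 labelled, p0 = 0.10 unlabelled, difference 0.05; power 80% (z = 0.8416); significance 5%; 10% labelled, so k = 9 unlabelled per labelled patient. Sidedness is not stated. Two-sided (z = 1.9600) is assumed because it reproduces the protocol's figure.

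**Step 1. Reproduce 1,372.** Pooled two-proportion formula, equal groups, mean risk 0.125:

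n per group = [1.9600 x √(2 x 0.125 x 0.875) + 0.8416 x √(0.15 x 0.85 + 0.10 x 0.90)]² / 0.05²

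= (0.9167 + 0.3925)² / 0.0025 = 685.6, rounded up to 686.

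2 x 686 = 1,372, an exact match. Other versions of the equal-groups total do not match: one-sided 1,080, unpooled 1,366, Hsieh's logistic formula 1,371, Wald log odds ratio 1,390, continuity-corrected 1,452. The 1,372 is therefore a two-group total that includes 686 unlabelled patients.

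**Step 2. Reproduce 13,720.** 1,372 / 0.10 = 13,720. This design has 1,372 labelled and 12,348 unlabelled patients.

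**Step 3. The same formula at 1:9.** Pooled risk P = (0.15 + 9 x 0.10) / 10 = 0.105.

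n labelled = [1.9600 x √(0.105 x 0.895 x 10/9) + 0.8416 x √(0.1275 + 0.09/9)]² / 0.05²

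= (0.6333 + 0.3121)² / 0.0025 = 357.5, rounded up to 358.

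Total = 358 + 9 x 358 = 358 + 3,222 = **3,580**.

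Unpooled formula: (1.9600 + 0.8416)² x 0.1375 / 0.0025 = 431.7 labelled, about **4,320** in total. Other formulas at 1:9 give 3,329 (Wald log odds ratio), 3,575 (Hsieh) and 3,800 (continuity-corrected). None approaches 13,720.

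**Step 4. Power of the label comparison, 15% v 10%, unadjusted, 10% labelled.**

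| Total | Labelled | Power, pooled | Power, unpooled |
|---|---|---|---|
| 3,580 | 358 | 80.0% | 72.3% |
| 4,320 | 432 | 86.3% | 80.0% |
| 6,000 | 600 | 94.5% | 91.0% |
| 13,720 | 1,372 | 99.95% | 99.88% |

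Worked for 13,720, pooled: the standard error of the difference is 0.008724 under no difference and 0.010011 under 15% v 10%. Then (0.05 - 1.9600 x 0.008724) / 0.010011 = 3.287, which gives 99.95%.

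**Step 5. What 13,720 detects at about 80% power.** For 12.5% v 10% with 1,372 labelled, power is 80.7% pooled and 76.4% unpooled.

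**Step 6. Check the primary calculation.** Dose is Poisson with mean 2; risk is 12% at dose 0 and 10% at dose 2, so the slope is [log(0.10/0.90) - log(0.12/0.88)] / 2 = -0.1024 per dose. Asymptotic power of the logistic Wald test is 89.8% at 6,000, so the stated 90% reproduces. At 13,720 it is 99.8%.

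**The case against.** The strongest reply is that the error is in the safe direction. It affects the principal secondary comparison, the primary calculation reproduces, and the study uses routine data with no intervention. Oversizing biases no estimate and puts no patient at risk; its cost is data collection at sites that this calculation does not require. All of that stands. It bears on how serious the error is, not on whether the sentence is correct.

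A larger cohort may also be wanted for multivariable adjustment, list-wise deletion or uncommon outcomes such as mortality and allergic reactions. That is reasonable, and it is why the point is not that 13,720 is too many patients for the study. But Section 9 does not offer these as the basis for 13,720, so they do not rescue the sentence.

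A charitable reading is that only the per-group figure was meant to be divided by 10%. That gives 686 / 0.10 = 6,860, half the stated total, and still 94 to 97% power rather than 80%.

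Some stronger readings are tempting but not supported:

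- A reader might infer that the study is roughly four times too large (13,720 / 3,580 = 3.8). That ratio concerns one unadjusted comparison taken alone. Against the larger of the protocol's own requirements, the ratio is 13,720 / 6,000 = 2.3.
- A reader might infer that 13,720 comes from nowhere. It follows directly from the second calculation as written; the step is what is invalid.
- A reader might see 10% as contradicting Section 6.1, which reports 12% for penicillin labels and "Up to 1 in 7 patients carries such a label". The latter is an upper bound, the 12% comes from elective patients while this cohort also includes fracture fixation and Caesarean section, and a lower prevalence is a conservative planning value. At 12% the pooled total would fall to about 3,058. There is no contradiction to correct.
- A reader might infer that recruiting fewer than 13,720 would leave the label comparison underpowered. Nothing in the protocol says what would follow from a shortfall, and the power at 6,000 shows that the inference would be wrong.

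**Conclusion.** The scaling step is wrong as written. The 1,372 is a two-group total, and dividing it by 10% gives a design with about 99.9% unadjusted power for 15% v 10%, not the stated 80%. The like-for-like requirement at 10% labelled is about 3,580 in total, or about 4,320 with the unpooled formula.

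The error oversizes the study and does not underpower it. On the protocol's own assumptions 6,000 is the larger of the two requirements.

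These figures rest on the stated 15% and 10% risks, 10% labelled, a two-sided 5% test (inferred from the exact match) and no allowance for covariate adjustment, clustering or missing data. The conclusion does not depend on the choice of formula: every version tried at 1:9 falls between 3,329 and 4,317.

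**What to change.** In Section 9, replace the tenfold step with the calculation for a 1:9 split. Name the formula and the sidedness, give the resulting total (about 3,580 pooled or about 4,320 unpooled), and state that the primary calculation of 6,000 is then the larger requirement.

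If 13,720 is kept, say so in Section 9 and the synopsis and give the actual rationale, for example covariate adjustment, missing data or rarer outcomes. Add what the target delivers before adjustment:

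- about 99.9% power for 15% v 10% by allergy label;
- about 76 to 81% power for 12.5% v 10%, depending on the formula;
- about 99.8% power for the primary dose effect.

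The cost is a few sentences in Section 9 and a matching line in the synopsis. No extra patients or data are needed.
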